1 STATEMENT OF COMPLIANCE

The trial will be carried out in accordance with International Conference on Harmonisation Good Clinical Practice (ICH GCP) and the following:

- United States (US) Code of Federal Regulations (CFR) applicable to clinical studies (45 CFR Part 46, 21 CFR Part 50, 21 CFR Part 56, 21 CFR Part 312, and/or 21 CFR Part 812)

The protocol, informed consent form(s), and recruitment materials will be submitted to the Institutional Review Board (IRB) for review and approval. Approval of both the protocol and the consent form must be obtained before any participant is enrolled. Any amendment to the protocol will require review and approval by the IRB before the changes are implemented to the study. In addition, all changes to the consent form will be IRB-approved; a determination will be made regarding whether a new consent needs to be obtained from participants who provided consent, using a previously approved consent form.

2 PROTOCOL VERSION HISTORY

The table below is intended to capture changes of IRB-approved versions of the protocol, including a description of the change and rationale. A Summary of Changes table for the current amendment is in the Protocol Title Page.

Version	Date	Description of Change	Brief Rationale
1.0	02NOV2021	Original protocol	N/A
1.1	02FEB2022	
Updated schedule of activities to include PHQ-9 question 9
 
Changed order of enrollment
 
2) Removed wording about 1:1:1:1 ratio of randomization
 
3) Added screenshot of Curebase sign up page
 
4) Added new demographic message in Communication Plan
 
5) Added verbiage in communication plan to confirm that participants have received their VR headset
 
6) Added option for participants to receive text notifications during the study in pre-screen survey
 
7) Added Pretreatment Survey Completion screen
 
8) Updated Support Protocol & Scripts
	
Ensures screening process is reflected in the SoA
 
Moving the shipment survey before the pre-treatment BPIs allows for simpler CSV data output
 
2) Randomization ratio is 2:1:2:1 on protocol
 
3) This is the account creation page for Curebase
 
4) Allows us to confirm if the participant has received the headset and confirms the start of the intervention
 
5) Ensures we receive demographic information from patients if they leave the website
 
6) All study notifications will be sent via email due to complexity of study and text message character limit. To reduce the number of notifications sent, participants will have the option to receive texts
 
7) Positive reinforcement for participants to complete pretreatment surveys
 
8) Updated questions and answers to reflect flow of study

2.0	04MAR2022	
 (1) Change randomization ratio to 1:1:1:1 (2) Updated name of PI from [name] to [name] (3) Added new Study Investigator [name]. (4) Updated the number of participants the study will enroll from 800 participants to 1000 (5) Add exclusion criteria: only one participant per household allowed to participate (6) Add exclusion criteria: recent or future medical procedures (7) Clarify language for payment schedule 	
 (1) Upon further investigation, we determined that a randomization of 1:1:1:1 would better suit the study and would help us reach the outcomes we want to achieve. It also allows for easier recruitment of participants and randomization through Curebase. (2) PI [name] is no longer part of AppliedVR (3) [name] is the new CMO for AppliedVR and will now be involved in the study monitoring (4) The increase in number of participants that will enroll is necessary due to the new change in randomization ratio (5) Protects integrity of study so that study details are not shared between household members (6) To adjudicate acute versus chronic pain. We are studying chronic pain therefore it is necessary to exclude acute pain diagnosis (7) Provide clarification that payment is tied to survey completion and not VR session completion
-----	-----------	---	--

5 LIST OF ABBREVIATIONS

Abbreviation	Definition
AE	Adverse Event
ADE	Adverse Device Effect
AVR	AppliedVR, Inc.
BPI	Brief Pain Inventory
CAP-6	Concerns About Pain
CBT	Cognitive Behavioral Therapy
CDC	Center For Disease Control and Prevention
CDRH	FDA Center for Devices and Radiological Health
CFR	Code of Federal Regulations
CID	Clinically Important Difference
CLBP	Chronic Low Back Pain
CONSORT	Consolidated Standards of Reporting Trials
COVID-19	Sars-cov-2 Coronavirus
CRF	Case Reporting Form
FDA	Food And Drug Administration
GCP	Good Clinical Practice
HIPAA	Health Insurance Portability and Accountability Act
ICH GCP	International Conference on Harmonisation Good Clinical Practice
IDE	Investigational Device Exemption
IRB	Institutional Review Board
JMIR	Journal Of Medical Internet Research
MCRA	Company Name: Regulatory Consultants
MHLC-C	Multidimensional Health Locus of Control
ODI-2.1b	Oswestry Disability Index
OUD	Opioid Use Disorder
PGIC	Patient Global Impression of Change
PHI	Protected Health Information
PHQ-9	Patient Health Questionnaire (9 Question Instrument)
PI	Principal Investigator
PMID	PubMed Identification
PROMIS	Patient-Reported Outcomes Measurement Information System
PSEQ-10	Pain Self-Efficacy Questionnaire (10 Question Instrument)
PUI	Perceptual User Interface
RCT	Randomized Controlled Trial
ROM	Read Only Memory
SAE	Serious Adverse Event
SUS	System Usability Scale
TMF	Trial Master File
UADE	Unanticipated Adverse Device Effect
USA	United States of America
VR	Virtual Reality

6 PROTOCOL SUMMARY

6.1 SYNOPSIS

Title:	A Decentralized, Randomized, Controlled Trial of EaseVRx-8w+ for Chronic Low Back Pain
Study Sponsor	AppliedVR, Inc. [name] [contact]
Study Investigators	[name] , PhD (Principal Investigator) [name] [name] [name]
Investigational Device	EaseVRx is a prescription-use immersive virtual reality system intended to provide a combination of biopsychosocial pain education, diaphragmatic breathing training, relaxation exercises, and executive function games for participants diagnosed with chronic low back pain (CLBP). The device is intended for in-home use for the reduction of pain and pain interference associated with CLBP.
Study Purpose	The aim of this randomized controlled trial (RCT) is to assess outcomes for virtual reality therapy (including pain intensity, pain interference, anxiety, depression, physical function, sleep, behavioral skills development, health outcomes and satisfaction) along with healthcare utilization and costs in participants with CLBP.

Study Design	
This is a decentralized, randomized controlled trial with four parallel study arms comparing change from pre-treatment to end-of-treatment to 12-months post-treatment in the EaseVRx-8w, EaseVRx-8w plus extended on-demand and Control groups.
 
After consenting to join the study, participants will be randomized and allocated to one of four treatment programs. Study devices will be delivered to the participant's home with instructions for use via FedEx with complementary remote technical support.
 
 • participants in the EaseVRx-8w arm will participate in an 8-week interventional program and continue to be followed for 24 months after completion of treatment • participants in the EaseVRx-8w plus extended on-demand arm will enroll in an 8-week interventional program and be offered an extended 8-week on-demand period, and continue to be followed for 24 months after the completion of treatment • participants in the first control arm will receive 2D Sham VR virtual reality content during the 8-week interventional program and continue to be followed for 24 months after the completion of treatment • participants in the second control arm will receive 2D Sham VR virtual reality content during the 8-week interventional program and be offered an extended 8-week on-demand period, after which they will continue to be followed for 24 months after the completion of treatment 
All trial participants will be monitored for pain intensity and pain interference, physical function, behavioral skills development, health outcomes and satisfaction.
 
Additionally, to assess resource use associated with CLBP, participant data will be run through a secure Datavant matching process to be linked to their healthcare claims data if it is available in the Komodo data set. The claims will provide descriptive characterizations of resource use and healthcare costs associated with CLBP. For participant-level changes in resource use, and for comparisons between study arms, only the participants with complete claims files will be assessed. Claims-matched data will capture all interactions with the healthcare system that generate an insurance claim record, which includes such things as physician visits, interventions such as steroid injections, surgery or physical therapy, emergent use of services, medications, and diagnostic procedures. Claims adjudication often lags a few months, so the most robust analyses of utilization will be performed about 6 months after the time point of interest. Health economic modeling will be performed after 1 year to assess the cost and economic outcomes of the EaseVRx intervention.


	The Komodo claims data provides a real-world source of utilization and cost parameters associated with claims of CLBP. As such, it can be used more broadly to either compare the study participants' resource use and costs to the broader population of participants with CLBP, or a "synthetic arm" can be constructed using available demographic data to match any of the study arms.
Study Duration	This study is expected to take approximately 36 months for completion.
Number of Participants & Sites	This study will enroll approximately 1000 participants using a fully decentralized direct-to-participant trial design without any central data collection sites.
Randomization Scheme	Enrolled participants will be randomized 1:1:1:1 and assigned to one of four treatment arms: 
 • 56-day skills-based VR program (EaseVRx-8w) • 56-day skills-based VR program followed by an extended 56-day on-demand period (EaseVRx-8w plus extended on-demand) • 56-day control (Sham VR) • 56-day control followed by an extended 56-day on-demand period (Sham VR plus 8w extended on-demand)
Evaluation Schedule	Participants in all 4 treatment arms will be evaluated at the following timepoints: pre-treatment, 2x/week during treatment, immediately post-treatment (day 56 in all arms), 4-weeks post-treatment, 8-weeks post-treatment, 12-weeks post-treatment, 6 months post-treatment, 12 months post-treatment, 18 months post-treatment, 24 months post-treatment.
Intended Participant Population	Mixed community-based sample and physician-referred sample of individuals aged 18 and older with a diagnosis of CLBP (defined as moderate to severe pain lasting longer than three months). Participant recruitment methods will aim to guarantee data collection from the following groups: 
 • At least 250 of the approximately 1000 recruited participants will be $\geq 65+$ years old. • At least 250 of the approximately 1000 recruited participants will be of lower education and socioeconomic status (based on education level, employment status and annual household income).
Enrollment Target	Approximately 1000 participants

Inclusion Criteria	
In order to be eligible to participate in this study, participants must meet all of the following criteria:
 
 1. Male and female adults aged 18-85. 2. Self-reported chronic low back pain that will be confirmed with claims data when available. 3. Pain duration of at least three months. 4. Average pain intensity score of ≥ 4 and average pain interference score of ≥ 4 on the 0-10 Brief Pain Inventory (BPI) Pain Scale for the past month at screening. 5. Fluency in English. 6. Willing and able to comply with all study procedures including all required restrictions for the duration of study participation. 7. Able to give voluntary, written informed consent to participate and have signed an Informed Consent Form specific to this study. 8. Access to Internet for the duration of their study participation (24 months). 9. Access to a smartphone or computer for the duration of the study. 10. Availability of a physical mailing address that is not a PO box address for receipt of the device. 11. Completed the Baseline Survey plus at least two of the five sets of participant surveys that are administered during the 10-day pretreatment assessment period. 12. Able to provide photo ID.
---------------------------	---

Exclusion Criteria	
Participants who meet any of the following criteria will be excluded from participating in this study:
 
 1. Unable to understand the goals of the study due to cognitive difficulty. 2. Any medical condition that may prevent the use of virtual reality (e.g., current, or prior diagnosis of epilepsy, seizure disorder, hypersensitivity to flashing light or motion, migraines, any medical condition predisposing participant to nausea or dizziness, dementia, absence of stereoscopic vision or severe hearing impairment). 3. Injury to eyes, face, or neck that prevents comfortable use of VR. 4. Index back pain is linked to a cancer-related diagnosis. 5. Possible suicidal ideation as indicated by the 9th item of the Participant Health Questionnaire-9 (PHQ-9). 6. Previous participation in the 2020 AVR EaseVRx pivotal study. 7. Receiving worker's compensation and/or involved in any active litigation related to an injury. 8. Current or recent participation (i.e., within the last 2 months) in any other research study involving a drug, device, vaccine, or other interventional treatment product; or plans to participate in another research study over the next 24 months. 9. Participation of two or more members in one household 10. Recent or future medical procedures scheduled related to any current diagnosis
Primary Objective	
The primary objective of this study is to evaluate the following:
 
Primary Endpoint: Assess the impact of skill-based VR on pain Intensity or Interference compared to sham VR.
 
 • Assess the effect of EaseVRx vs. Sham VR on group score change from baseline to end of treatment on pain intensity • Assess the effect of EaseVRx vs. Sham VR on group score change from baseline to end of treatment on pain interference

Secondary Objectives	
The secondary objectives of this study include the following:
 
 1. Assess the effect of EaseVRx vs. Sham VR by comparing: 
 • Percentage of participants with a $\geq 30\%$ change in pain intensity measured with the Brief Pain Inventory (BPI) from pre-treatment to end-of-treatment (8 weeks) for each group • Percentage of participants with a $\geq 30\%$ change in pain interference measured with the BPI (as represented by a single composite score derived from 7 pain interference questions) from pre-treatment to end-of-treatment (8 weeks) for each group 2. Assess the effect of EaseVRx vs. Sham VR by comparing: 
 • Change in Oswestry Disability Index (ODI-2.1b), PROMIS Sleep Disturbance, PROMIS Depression and PROMIS Anxiety from pre-treatment to end-of-treatment (8 weeks) for each group 3. Assess effect of EaseVRx vs. Sham VR by comparing participant satisfaction at end-of-treatment (8 weeks) for each group
Exploratory Objectives	
The exploratory objectives of this study include the following:
 
 1. Assess the impact of skill-based VR in follow-up pain adjusting for baseline pain. 2. Assess the impact of skill-based VR based on clinical importance changes in a responder framework. This endpoint is included to provide sensitivity around the secondary endpoint. 3. Assess the impact of skill-based VR on changes in healthcare utilization and outcomes throughout an 8-week intervention and follow-up period. 4. Assess effect of EaseVRx vs. Sham VR by comparing change in Concerns About Pain (CAP-6); and behavioral skills from pre-treatment to end-of-treatment for each group. 5. Assess effect of EaseVRx vs. Sham VR by comparing participant Global Impression of Change (PGIC) and system usability (as measured with the System Usability Scale; SUS) at end-of-treatment for each group. 6. Assess effect of EaseVRx vs. Sham VR by comparing change in all objectives from pre-treatment to end-of-treatment, 4 weeks post treatment, 8 weeks post treatment, 12 weeks post treatment, 6 months post treatment, 12 months post treatment, 18 months post treatment and 24 months post treatment in the EaseVRx-8w and EaseVRx-8w plus extended on-demand groups.
Clinical Research Organization (CRO)	
MCRA, LLC [name]

6.2 SCHEDULE OF ACTIVITIES (SoA)

VISITS	re-Treatment		Treatment		Post-Treatment (PT)						
	Day - 10 ¹	Day -9 to 0	Wks. 1-8	Day 56	4 Wks. (84 +7 days) ¹	8 Wks. (112 +7 days) ¹	12 wks. (140 +7 days) ¹	6 months (238 +30 days) ¹	12 months (420 +30 days) ¹	18 months (602 +30 days) ¹	24 months (784 +30 days) ¹
Pre-Screener	X										
Suicidality Screener - 9th item of PHQ-9	X										
Demographic survey	X										
Informed Consent via Curebase	X										
Identity Verification	X										
Brief Pain Inventory (BPI) pain intensity/interference	X	X ²	X ³	X	X	X	X	X	X	X	X
Oswestry Disability Index	X			X	X	X	X	X	X	X	X
PROMIS Sleep Disturbance	X			X	X	X	X	X	X	X	X
PROMIS Depression	X			X	X	X	X	X	X	X	X
PROMIS Anxiety	X			X	X	X	X	X	X	X	X
Concerns About Pain (CAP-6) Scale	X			X	X	X	X	X	X	X	X
Behavioral Skills Use	X			X	X	X	X	X	X	X	X
Participant's Global Impression of Change Scale (PGIC)				X	X	X	X	X	X	X	X
Pain Self-Efficacy Questionnaire (PSEQ-10)	X ¹			X ¹	X ¹	X ¹	X ¹	X ¹	X ¹	X ¹	X ¹
Multidimensional Assessment of Interoceptive Awareness (Ver 2)	X ¹			X ¹	X ¹	X ¹	X ¹	X ¹	X ¹	X ¹	X ¹
Multidimensional Health Locus of Control	X ¹			X ¹	X ¹	X ¹	X ¹	X ¹	X ¹	X ¹	X ¹
VR Sickness Questionnaire		X ⁴	X ⁴	X ⁴	X ⁴						
participant Satisfaction			X								
System Usability Scale (SUS)			X								
Benefits Screening								X			
Shipping Address Survey	X										
EaseVRx User Experience Questionnaire			X			X ⁵					
Randomization (performed within Curebase portal)		X									
Ship Intervention kit to participants		X									
Technical onboarding	X										
Record VR compliance/use data ⁶		X	X	X ⁵	X ⁵						
Collect study intervention kit							X				
Perceived Treatment Assignment			X								
Healthcare utilization data analysis			X ⁷	X ⁷	X ⁷	X ⁷	X ⁷	X ⁷	X ⁷	X ⁷	X ⁷

¹ OPTIONAL survey offered next day.

² Two out of five BPI survey instances to be completed over 9-day pre-intervention period.

³ Research staff will monitor participants' progress through twice weekly BPI surveys.

⁴ VR Sickness Questionnaire will be administered once per week during treatment and once per week for the 16-week arms.

⁵ For participants assigned to extended 56-day on-demand period only.

⁶ Device use to be monitored on a weekly basis when participants connect the device to Wi-Fi. For participants who do not connect their headset to Wi-Fi, compliance will be assessed post-intervention when the headset has been returned.

⁷ Komodo data analysis to begin after all participants have completed Day 56 and will be ongoing through 24-month post-treatment visit.

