11.6 POST-TREATMENT DATA COLLECTION

After Day 56, participants will be prompted to log onto the Curebase portal and complete the following assessments at 4-weeks, 8-weeks, 12-weeks, 6-months, 12-months, 18-months, and 24-months post-treatment:

- Brief Pain Inventory - intensity/interference
- Oswestry Disability Index
- PROMIS Sleep Disturbance
- PROMIS Depression
- PROMIS Anxiety
- participant's Global Impression of Change Scale (PGIC)
- Concerns About Pain (CAP-6) Scale
- Behavioral Skills Use

Data Completion Reminders: Participants will be sent a reminder if they have not submitted data approximately 1 hour after starting a survey. Participants will also receive a reminder email or text message if they do not submit data approximately 24 hours after starting a survey. Research staff will make up to 3 call attempts to contact the participant to help get these surveys completed.

Twenty-four hours after completing the surveys listed above, participants will be contacted with information about completing an optional incentivized set of surveys that include the following:

- Pain Self-Efficacy Questionnaire (PSEQ-10)
- Multidimensional Assessment of Interoceptive Awareness (Version 2)
- Multidimensional Health Locus of Control

Reminders will be sent approximately 1 hour and 24 hours after starting a survey to encourage optional survey completion.

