16 SAFETY REPORTING

Participants will be carefully monitored during the study for possible adverse events (AEs) from the time they start treatment or sham to the time of study completion. All medical events and conditions prior to

this time point are to be captured as medical history. Any observed AE will be fully investigated by the Investigator and classified in line with the definitions below.

All adverse events that occur during this study will be recorded on the adverse event eCRFs and must include the following information at minimum:

- Event Description
- Date of Onset
- Date of Resolution
- Severity
- Seriousness
- Relationship to Study Device/Procedure
- Outcome

Adverse events will be recorded and classified by the research team, including a medical doctor on staff, using the specific signs, symptoms, or medical diagnosis if no signs or symptoms can be identified.

Significant new information and updates should continue to be captured in the participant's records and in the EDC as they become available and the adverse event should be followed until it is resolved or no further improvement is expected, or the participant is lost to follow-up. The Investigator will record all AEs regardless of whether they are anticipated or unanticipated and regardless of classification, seriousness, intensity, outcome, or causality.

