16.4 ADVERSE EVENT REPORTING

The collection of AEs will begin as soon as the participant first puts on the VR headset for this study. All AEs that occur through completion of the final follow-up visit, whether or not thought to be device related, should be recorded in detail and followed to resolution.

The description of the AE will include the date and time of onset, severity, relationship to the use of the device, the results of any diagnostic procedures or laboratory tests, if any treatment was required, and the outcome of the event. The AVR research team will follow each participant who experiences an AE until the event resolves, resolves with sequelae, or no further improvement is expected. In the unusual circumstance that an AE has not resolved by the time the participant completes the study, an explanation will be entered in the study database.

Note: Any condition at baseline that is recorded as a preexisting condition is not an AE unless it worsens in intensity or duration.

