3.2 SAFETY ANALYSIS

Assessment of the safety of the investigational device will include an evaluation of the incidence and severity of complications and adverse reactions associated with the treatment. Primary safety comparisons will be performed using the mITT analysis set.

Adverse event rates will be summarized by type of AE and for specific AEs in two ways:

1. Per subject incidence of specific AEs and classes of AEs
2. By event, summarizing event counts by visit interval over time and in accordance with FDA Guidance (CDRH 2004).

Events will be summarized by severity and relatedness.

The summary tables will show the adverse events (in coded terms), the total number of events, and the number and the percentage of subjects affected in the investigational group

(“subject wise evaluation”) and stratified by relation to device and severity. Data of dropouts will not be presented separately, but possible bias will be discussed in the final report.

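### No general adverse-event enquiry is scheduled at any visit, although all AEs must be recorded to 24 months; 86% to 93% of that period falls after the last cybersickness form

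*Protocol*

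**What the plan says.** The safety commitment is broad. Protocol Section 16 undertakes that everyone treated is "carefully monitored during the study for possible adverse events (AEs) from the time they start treatment or sham to the time of study completion". Section 16.4 fixes the start ("The collection of AEs will begin as soon as the participant first puts on the VR headset for this study") and the scope and end ("All AEs that occur through completion of the final follow-up visit, whether or not thought to be device related, should be recorded in detail"). Neither section names a question, an instrument or a frequency for finding these events.

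The Schedule of Activities in Section 6.2 lists items as minor as the shipping-address survey and kit collection, but has no AE or SAE row. Its repeated symptom instrument is set out in footnote 4: "VR Sickness Questionnaire will be administered once per week during treatment and once per week for the 16-week arms". Section 14.1 describes this as a 12-item form on symptoms such as dizziness and nausea.

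After Day 56, Section 11.6 has participants "complete the following assessments at 4-weeks, 8-weeks, 12-weeks, 6-months, 12-months, 18-months, and 24-months post-treatment". The list that follows is BPI, ODI, three PROMIS scales, PGIC, CAP-6 and behavioral skills, with optional questionnaires the next day. The Day 56 list in Section 11.5 likewise contains no general AE item.

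SAP Section 3.2 plans per-subject incidence and a second tabulation: "By event, summarizing event counts by visit interval over time".

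**The concern.** The trial has no central data collection sites (Section 6.1), so no clinic visit exists at which a coordinator would routinely ask what has happened since the last contact. If the listed surveys are run exactly as written, no general question about new illness, emergency care or hospital admission is put to participants during treatment or follow-up.

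Three things are at stake.

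- The AE and SAE tables in SAP 3.2 would tend to under-count, and the counts would partly reflect who makes contact.
- The sponsor's review for unanticipated adverse device effects (Section 16.6) works from SAEs that have been reported. An SAE that no one reports does not enter it.
- In Weeks 9-16 the on-demand arms still receive a weekly symptom form and the 8-week arms do not. Ascertainment therefore differs when on-demand arms are compared with 8-week arms.

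**Working it through.** **Inputs**

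- AE collection starts at first headset use, taken as about Day 0 (Section 16.4).
- AE collection ends at the 24-month visit, Day 784 with a +30-day window (Sections 16.4 and 6.2).
- The VR Sickness Questionnaire ends at Day 56 in the 8-week arms and Day 112 in the on-demand arms (Section 6.2, footnote 4). Timing is taken from the footnote because the column alignment of the table marks could not be relied on.

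**Check of the plan's visit days.** Visit day = 56 + 7 × weeks post-treatment. With 4, 8, 12, 26, 52, 78 and 104 weeks this gives 84, 112, 140, 238, 420, 602 and 784. All seven match the schedule.

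**Share of the collection period after the last symptom form** = (end day − last form day) / end day

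- 8-week arms: (784 − 56)/784 = 728/784 = 92.9%
- On-demand arms: (784 − 112)/784 = 672/784 = 85.7%
- Average under 1:1:1:1 allocation: (92.9 + 85.7)/2 = 89.3%

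**Sensitivity**

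- End at Day 814 (full window): 758/814 = 93.1% and 702/814 = 86.2%.
- On-demand arms followed for 24 months after a 16-week treatment period, as Section 9.4 can be read: 112 + 728 = 840, and 728/840 = 86.7%.
- Last form at the 4-week visit (Day 84): 700/784 = 89.3%.

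The range of about 86% to 93% holds under each reading. It is a share of calendar time. It credits the sickness form with covering the device period, although that form would not pick up events outside its 12 symptoms.

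**Spacing of later surveys.** The gaps from Day 56 onward are 28, 28, 28, 98, 182, 182 and 182 days. None of these surveys is described as asking about AEs.

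**What else could bring an event to light**

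- Participant Satisfaction (Section 14.1): the heading mentions adverse effects, but the topics named are usability, enjoyment or difficulties, and willingness to continue. Given once, on Day 56.
- Outcome scales read with Section 13.1: a clinically relevant change from baseline is to be recorded as an AE, so worsening on a scale could lead to a record. An unrelated hospital stay would not show.
- Discontinuation of Treatment Questionnaire (Section 14.1): used only once a moderate AE has occurred, so it does not detect one.
- Reason for withdrawal (Section 13.2): asked only of those who leave.
- Claims linkage (Sections 11.7 and 14.3): care associated with low back pain, in a subset with complete files, analysed with a lag of about 6 months. Section 16 does not use it as an AE source.
- AE eCRFs (Section 16): these document a known event. They do not elicit one.

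**The case against.** The plan's authors could reply that AE collection belongs to Section 16 and its eCRFs, so the lack of a schedule row does not prove that nothing is asked. The version history (Section 2) mentions a communication plan and support scripts that are not part of these documents and might contain prompts or reporting instructions. Section 7.7.3 promises that cybersickness and discomfort are assessed after one week and watched closely. Staff also follow the twice-weekly BPI, telephone about unreturned devices and try to reach participants before declaring them lost. Section 7.7.1 anticipates no long-term risk, so a share of calendar time is not a share of device-relevant events.

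Much of this stands, and it rules out several stronger readings that a reader might infer:

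- That no visit asks anything about harm. The weekly sickness form and the heading of the Day 56 satisfaction survey contradict this. The satisfaction items are not reproduced, so their AE content cannot be judged.
- That later events come to light only if participants volunteer them. Section 13.1, withdrawal reasons and claims are partial routes. Section 7.6 says staff will also make contact when surveys are missing; it does not limit contact to that.
- That the main safety comparison is biased by the Weeks 9-16 prompting. One EaseVRx arm and one Sham arm receive those prompts under equal allocation, so pooled EaseVRx versus Sham is balanced.
- That interval counts simply follow the contact pattern. Onset date is a required field, so an event reported late can be placed in the correct interval.
- That a number of missed SAEs can be calculated. The documents give neither an SAE rate nor a volunteering rate.

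What this reply does not supply is a scheduled general enquiry. Section 16 cites no operational plan that contains one, and three separate lists (Sections 6.2, 11.5 and 11.6) agree in omitting it.

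**Conclusion.** The point holds in this form: the Protocol commits to recording all AEs to Day 784 but schedules no general AE or SAE enquiry at any visit. After the cybersickness form stops, 92.9% of the collection period remains in the 8-week arms and 85.7% in the on-demand arms. Over that time the partial sources would not reliably reveal an unrelated SAE or feed the review in Section 16.6.

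This goes beyond missing detail, because following the listed surveys as written would be expected to under-ascertain AEs and SAEs. By how much cannot be estimated from the documents. The primary endpoint is unaffected, and the uneven prompting matters only for on-demand versus 8-week comparisons.

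The conclusion assumes that footnote 4 gives the end of the sickness form correctly and that no unseen communication or support document already contains a scheduled AE question. If one does, the schedule should cite it.

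**What to change.** Add an Adverse Events row to the Schedule of Activities and the same item to Sections 11.4, 11.5 and 11.6. The item is one yes/no question on any new or worsened health problem, emergency visit or hospital stay since the last survey, with the date and whether it is ongoing. Attach it to one existing BPI survey per week in Weeks 1-8, to Day 56, and to all seven post-treatment surveys, with identical wording and timing in all four arms. A yes answer opens the AE eCRF.

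In SAP 3.2, tabulate all AEs by onset date and flag each as prompted or volunteered.

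The cost is one extra survey screen in Curebase, more AE records to process, and an IRB amendment. No visits are added.
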